4.2 Phase II

Phase II will be a prospective, open label, interventional study with previously treated HER2-negative metastatic breast cancer and metastatic inflammatory breast cancer patients. Subjects receive capmatinib in combination with neratinib. The MTD determined during Phase 1b will be used.

This portion of the trial will be conducted to assess the overall response rate (ORR) for patients treated at the MTD. The target ORR will be 25%, with unacceptable ORR as 5%. We will assess the ORR using the Bayesian optimal phase 2 (BOP2) design (Zhou, Lee and Yuan, 2017).

Up to an additional 29 evaluable subjects with measurable disease will be enrolled. An interim analysis will be performed when the number of enrolled patients reaches 15.

The study Phase II portion safety and efficacy data will be monitored by the IND Office.

Treatment response will be evaluated per RECIST tumor response through QIAC.

4.3. Subject Population to be included:

In the Phase 1b portion of the study, previously treated HER2-positive and HER2-negative, HR-positive and HR-negative metastatic and inflammatory breast cancer patients will be enrolled.

In the Phase II portion of the study, previously treated HER2-negative, HR-positive and HR-negative metastatic and inflammatory breast cancer patients with abnormal HER-family and c-Met signaling tumors will be enrolled. The CELsignia Multi-Pathway (CELsignia MP) Test will characterize the subjects' HER-family and c-Met-driven signaling pathways as either hyperactive or normally active.

4.4 Number of Subjects per Study Group:

Phase Ib

This portion of the study will enroll a maximum of 18 patients in the dose-finding trial including the possibility of adding up to 6 additional ER+ HER2 negative patients in a safety assessment of aromatase inhibitor treatment. The statistical considerations used to derive this sample size are presented in Section 13.1.

Phase II

This portion of the study will enroll a maximum of 29 patients. The statistical considerations used to derive this sample size are presented in Section 13.2.

Total accrual of this study will be up to 47 patients. We plan the enrollment for Phase Ib dose escalation to be 1-3 per 2 months since the DLT observation period is 2 months; and for Phase II to be 0-2 per month for each open site.

5.0 Study Endpoints

5.1 Primary Endpoints

- **Safety**

The primary safety endpoint is to determine the safety, tolerability, and dose limiting toxicities (DLT) (Phase 1b) of the combination of capmatinib and neratinib, and of neratinib + capmatinib in combination with an aromatase inhibitor in ER+ MBC.

- **Efficacy**

For the Phase 2 portion of the study, the primary efficacy endpoint is overall response rate (ORR), defined as the rate of patients who achieve partial response or complete response as the best response.

All tumor response will be evaluated by RECIST 1.1 and measured by QIAC system, via research collaboration.

5.2 Secondary Endpoint(s):

- **Clinical benefit rate (CBR)**

Defined as the rate of patients who achieved complete response, partial response and stable disease for ≥ 24 weeks as the best response of treatment.

- **Duration of response (DOR)**

DOR is defined as the period measured from the date of the first occurrence of a CR or PR (whichever status is recorded first) until the first date that progressive disease or death is documented. Patients who have not progressed and who have not died by the date of data cutoff for analysis will be censored at the time of last tumor assessment date. If tumor assessments performed after the date of the first occurrence of a CR or PR showed a different response, DOR will be censored at the date of the first occurrence of a CR or PR plus remaining stable response from that time point.

- **Progression free survival (PFS)**

PFS is defined as the time between date of treatment start to the date of documented disease progression or death, whichever occurs first. Data from patients who have not experienced disease progression or death will be censored at the last tumor assessment date known to be free of disease progression. Data from patients with no post-baseline tumor assessment will be censored at the treatment start date plus 1 day.

- **2 year overall survival (OS)**

2 year OS definition: the proportion of patients in the study who are alive 2 years after enrollment on to the study.

5.3 Exploratory Endpoints:

- For exploratory purposes, ORR, CBR, DOR, PFS, and OS will also be analyzed separately for the sub-group of IBC patients and for the sub-group of advanced or metastatic non-IBC breast cancer patients.
- Assess response per molecular subtype, Hormone Receptor positive (ER and/or PR), HER2 negative and Triple Negative Breast Cancer
- Assess genomic profile of cancers treated on study to explore potential mechanisms of response and resistance.

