Study Endpoints	
Primary Endpoints:
 
 Safety The primary safety endpoint is to determine the safety, tolerability, and dose limiting toxicities (DLT) (Phase 1b) of the combination of Neratinib + Capmatinib in ER- MBC and of Neratinib + Capmatinib in combination with an aromatase inhibitor for ER+ MBC. Efficacy For the Phase 2 portion of the study, the primary efficacy endpoint is overall response rate (ORR), defined as the rate of patients who achieved partial response or complete response as the best response. All tumor response will be evaluated by RECIST 1.1 and measured by QIAC system, via research collaboration. 
Secondary Endpoint(s):
 
 Clinical benefit rate (CBR) Defined as the rate of patients who achieved complete response, partial response and stable disease for ≥ 24 weeks as the best response of treatment. Duration of response (DOR) DOR is defined as the period measured from the date of the first occurrence of a CR or PR (whichever status is recorded first) until the first date that progressive disease or death is documented. Patients who have not progressed and who have not died by the date of data cutoff for analysis will be censored at the time of last tumor assessment date. If tumor assessments were performed after the date of the first occurrence of a CR or PR showed different response, DOR will be censored at the date of the first occurrence of a CR or PR plus remaining stable response from that time point. Progression free survival (PFS) PFS is defined as the time between date of treatment start to the date of documented disease progression or death, whichever occurs first. Data from patients who have not experienced disease progression or death will be censored at the last tumor assessment date and known to be free of disease progression. Data from patients with no post-baseline tumor assessment will be censored at the treatment start date plus 1 day. 2 year overall survival (OS) 2 year OS definition: the proportion of patients in the study who are alive 2 years after enrollment on to the study 
Exploratory Endpoints:
 
 For exploratory purposes, ORR, CBR, DOR, PFS, and OS will also be analyzed separately for the sub-group of IBC patients and for the sub-group of advanced or metastatic non-IBC breast cancer patients. Assess response per molecular subtype, Hormone Receptor positive (ER and/or PR) and Triple Negative Breast Cancer Assess genomic profile of cancers treated on study to explore potential mechanisms of response and resistance.

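### The Synopsis and Section 5.2 censor duration of response on an undefined change in response, at a date that is not uniquely determined; Section 13.2 has no such rule

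*Combined protocol and SAP*

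**What the plan says.** **Synopsis and Section 5.2.** DOR runs from the first CR or PR "until the first date that progressive disease or death is documented". Patients with neither event by data cutoff "will be censored at the time of last tumor assessment date". A further sentence follows. In 5.2 it reads "If tumor assessments performed after the date of the first occurrence of a CR or PR showed a different response, DOR will be censored", and the censoring date is the first CR or PR date "plus remaining stable response from that time point". The Synopsis version is almost the same: "If tumor assessments were performed after the date of the first occurrence of a CR or PR showed different response, DOR will be censored". Neither the kind of change meant nor the added period is defined there or in the response criteria of Section 11.

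**Section 13.2.** DOR has the same start and the same event. The extra sentence is absent. Times are censored only where the event has not occurred by the analysis, and for DOR and PFS the date is the last contact at which the patient was known to be progression-free. DOR, PFS and OS are summarised by Kaplan-Meier, with medians, means and 95% confidence intervals.

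**PFS.** Section 5.2 states "PFS is defined as the time between date of treatment start to the date of documented disease progression or death, whichever occurs first". Event-free patients "will be censored at the last tumor assessment date known to be free of disease progression". It adds: "Data from patients with no post-baseline tumor assessment will be censored at the treatment start date plus 1 day". Section 13.2 does not carry that last rule.

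**The concern.** A time-to-event endpoint needs one event, one start and one censoring rule. Here an analyst working from 5.2 and one working from 13.2 can code the same patient differently, and two analysts who both follow 5.2 can still disagree on the date.

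The most plausible trigger is loss of PR to SD. Under that reading follow-up stops because the response was lost. Loss of response may be related to coming progression, so the censoring may be informative, and Kaplan-Meier assumes that it is not. If the trigger is instead an improvement from PR to CR, continuing responders are cut short.

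At stake are the reported DOR values. There will be few responders and the trial is open label, so the rule should be settled before the data are seen.

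**Working it through.** The documents give no DOR figure to reproduce. The check is a comparison of the sections, a test of whether the PR-to-SD path can occur, and two illustrations on assumed data.

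**1. Can a patient pass from PR to SD before progression?** Section 11.1 sets PR at a 30% or greater fall from the baseline sum B, so PR is lost when the sum exceeds 0.70B. Progression on target lesions needs both a 20% and a 5 mm increase over the nadir N, so the sum must reach the larger of 1.2N and N + 5 mm. SD can come between if that threshold lies above 0.70B.

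- The 20% part: 1.2N > 0.70B gives N > 0.583B, a best shrinkage below 41.7%.
- The 5 mm part: N + 5 > 0.70B gives a best shrinkage below 30% + 5/B (B in mm).
- The two limits meet at B = 5/(0.417 − 0.300), about 43 mm.

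| Baseline sum | Best shrinkage for which SD can come between |
|---|---|
| about 43 mm or more | 30% to 41.7% |
| 30 mm | 30% to 46.7% |
| 20 mm | 30% to 55% |

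The path is open under the protocol's own criteria, and is wider for small tumour sums. New lesions count as progression and bypass SD.

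**2. One patient under each rule.** Scans fall every 2 cycles, that is 56 days (Section 7.10, note d). Assumed course: PR day 0, PR day 56, SD day 112, SD day 168, progression day 224.

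| Rule | DOR |
|---|---|
| 13.2 | event at 224 days |
| 5.2 clause, date = first response | censored at 0 days |
| 5.2 clause, date = last scan still in response | censored at 56 days |
| 5.2 clause, date = end of stable disease | censored at 168 days |

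**3. Number of responders.** 29 × 0.25 = 7.25 at the target ORR; 29 × 0.15 = 4.35; 29 × 0.05 = 1.45.

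**4. Effect on a median.** Assume seven responders with progression at weeks 8, 16, 24, 32, 40, 56 and 72. The median is taken as the first time the Kaplan-Meier estimate is 0.5 or less.

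- *Plain rule:* after the fourth event the estimate is 3/7 = 0.43, so the median is 32 weeks.
- *Upper end:* the patients progressing at weeks 32 and 40 show SD one scan earlier and are censored at their last response scans, weeks 16 and 24. The estimate is 6/7 = 0.857 at week 8, 0.857 × 5/6 = 0.714 at week 16, 0.714 × 3/4 = 0.536 at week 24 and 0.536 × 1/2 = 0.268 at week 56. The median is 56 weeks.
- *Lower end:* the patients progressing at weeks 56 and 72 show SD at the first scan after response and are censored at the first response date. Five remain, and the estimate is 4/5, 3/5 and then 2/5 at week 24. The median is 24 weeks.

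Over all 15 pairs among the six patients progressing after week 8, the median is 32, 40 or 56 weeks if SD comes one scan before progression, and 24, 32 or 40 weeks if SD comes at the first scan after response. If instead the one or two longest responders are censored for PR to CR, it is 24 or 32 weeks.

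**5. The ordinary censoring date.** Section 5.2 uses the last tumour assessment and 13.2 the last progression-free contact. These agree if progression-free status must be shown by imaging. If an on-treatment visit suffices, visits come every 28-day cycle and scans every second cycle, so the dates can differ by about one cycle.

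**The case against.** The strongest defence is that the sponsor meant to censor at the last assessment still in response, and that 13.2 is only a summary. That intent is possible, so the date is better called not uniquely determined than unknowable. But the text does not say it, and the defence does not remove the conflict: that reading still stops follow-up when response is lost, while 13.2 counts the later progression.

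It is also fair to say that DOR is secondary, has no decision rule, and would be imprecise with about seven responders whatever the wording. That limits the consequence, not the inconsistency.

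Three stronger readings are tempting but not supported.

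- *Progression itself is censored.* Taken literally, progression is a changed response, and no progression event would then remain. But the same paragraph makes progression the event, and the clause follows a sentence on patients without one. This is unlikely to be the intent.
- *The two censoring dates can lie as far apart as the follow-up contacts.* Contacts after treatment come about every 6 months (Section 7.7), but they collect survival and new anticancer therapy. Such a contact does not by itself show that a patient is progression-free.
- *The PFS rule for patients without a post-baseline scan censors deaths.* It has no stated exception for death, but it follows a sentence limited to patients without progression or death, and death is already a PFS event. Its absence from 13.2 is an omission to repair, not a contradiction.

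**Conclusion.** The DOR rule is wrong as written. The Synopsis and 5.2 contain a censoring sentence with an undefined trigger and no unique date. Section 13.2 has no such sentence, and I found no text that says which section governs. The same patient can be an event under one section and censored under another.

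The size cannot be fixed from the documents. The 24-to-56-week spread around a 32-week median rests on assumed progression times and on which one or two patients are affected; it shows sensitivity and is not an estimate of bias. A reader might infer that DOR would be systematically lengthened. The examples move it both ways, so that does not follow. The difference in the ordinary censoring date for DOR and PFS is a smaller mismatch.

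Only secondary endpoints are affected. This should be corrected before analysis, but it does not bear on the trial's primary conclusion.

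**What to change.** - Delete the sentence on a different response from the Synopsis and Section 5.2.
- State that first documented progression or death is the only DOR event, whatever CR, PR or SD is recorded in between.
- In the Synopsis, 5.2 and 13.2, censor event-free patients for DOR and PFS at the last progression-free tumour assessment.
- As a clarification, carry the PFS rule for patients with no post-baseline assessment (treatment start plus 1 day) into 13.2, and say in all three places that it applies only to patients who have not died.

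The cost is two or three sentences of wording. Reported DOR may move in either direction. How scans after the start of new anticancer treatment are handled is a separate question that this change does not settle.

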6.0 Eligibility Criteria

6.1 Inclusion Criteria

1. Signed Informed Consent Form (ICF) and comply with the requirements of the study protocol
2. Age \geq 18 years.
3. ECOG performance status 0-1
4. Confirmed diagnosis of metastatic breast cancer or inflammatory breast cancer according to international consensus criteria³⁰:
 - Onset: Rapid onset of breast erythema, edema, and/or peau d'orange, and/or warm breast, with or without an underlying breast mass
 - Duration: History of such findings no more than 6 months
 - Extent: Erythema occupying at least 1/3 of whole breast
 - Pathology: Pathologic confirmation of invasive carcinoma
5. Patients who have metastatic disease which is not amenable to curative treatment with available local and systemic therapy. Patients must have received at least 1 line or up to 6 lines of therapy in the metastatic setting with at least 2 weeks washout period before the initiation of study treatment.
 - i. Unless a contraindication to therapy exists, patients with ER+ breast cancer must have received prior endocrine therapy combined with a CDK4/6 inhibitor, patients with *BRCA1* or *BRCA2* mutations must have received prior PARP inhibitor, and patients with PD-L1+ triple negative breast cancer must have received prior immunotherapy.
 - ii. Patients with HER2-positive disease must have received at least 2 regimens of anti-HER2 therapy in metastatic setting.

6. For Phase Ib, any ER, PR, and HER2 status, For Phase 2, HER2-negative per ASCO/CAP guidelines and any ER and PR status.

7. For Phase II only, Patients with measurable disease according to the Response Evaluation Criteria in Solid Tumor (RECIST, v1.1) (local or distant) and at least one metastatic lesion amenable for biopsy (core or punch)

NOTE:

Measurable disease: Measurable lesions are defined as those that can be accurately measured in at least one-dimension (longest diameter to be recorded) as ≥ 20 mm by chest X-ray, ≥ 10 mm by computed tomography (CT) scan, ≥ 10 mm with calipers by clinical exam.

Measurable malignant lymph nodes: To be considered pathologically enlarged and measurable, a lymph node must be ≥ 15 mm in short axis when assessed by CT scan.

Non-measurable disease: All other lesions (or sites of disease), including small lesions, are considered non-measurable. Bone lesions, leptomeningeal disease, ascites, pleural/pericardial effusions, lymphangitis, cutis/pulmonitis, inflammatory breast disease, and abdominal masses [not followed by CT or magnetic resonance imaging (MRI)] are considered non-measurable.

8. Left Ventricular Ejection Fraction $\geq 50\%$ measured by MUGA scan or Echocardiogram.

9. Abnormal HER-family and c-Met signaling activity based on CELsignia MP Test results (for phase II patients only).

10. Participants must have adequate organ function including the following laboratory values at the screening visit. Screening must occur within 28 days prior to the first dose of study drug. Screening samples for hematology and serum chemistries must be drawn within 14 days prior to the first dose of study drug:

- Absolute neutrophil count (ANC) $\geq 1.5 \times 10^9/L$ without growth factor support
- Platelets (PLT) $\geq 75 \times 10^9/L$
- Hemoglobin (Hgb) $\geq 9 \text{ g/dL}$
- Calculated creatinine clearance (using Cockcroft-Gault formula) $\geq 45 \text{ mL/min}$
- Total bilirubin (TBIL) $\leq \text{ULN}$ (upper limit of normal) with the following exception: Patients with known Gilbert disease who have serum bilirubin level $\leq 3 \times \text{ULN}$ may be enrolled.
- Aspartate transaminase (AST) $\leq 3 \times \text{ULN}$, except for participants with liver metastasis, who may only be included if AST $\leq 5 \times \text{ULN}$
- Alanine transaminase (ALT) $\leq 3 \times \text{ULN}$, except for participants with liver metastasis, who may only be included if ALT $\leq 5 \times \text{ULN}$
- Alkaline phosphatase (ALP) $\leq 5.0 \times \text{ULN}$

- Asymptomatic serum amylase \leq grade 2. Participants with grade 1 or grade 2 serum amylase at the beginning of the study must be confirmed to have no signs and/or symptoms suggesting pancreatitis or pancreatic injury (e.g., elevated P-amylase, abnormal imaging findings of pancreas, etc.)
- Serum lipase \leq ULN

11. Willing and able to comply with scheduled visits, treatment plan and laboratory tests. Patients who are cognitively impaired who may not be able to comply with the oral study medication schedule are excluded.

- i) Patients with ER positive (defined at ER $>/=10\%$)breast cancer, must start (or continue) an aromatase inhibitor of physician choice during the study duration. In addition, pre-/peri-menopausal women with ER+ breast cancer will also require ovarian suppression therapy.

12. Non-English speaking subjects are eligible as long as a translator is available at the treating site.

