7.3 General Treatment Guidelines

If a toxicity is attributed to one of the study drugs, it may be held and the other drug(s) will still be given as scheduled. If a toxicity is not clearly linked to a single drug, then both neratinib and capmatinib may be held. The treating physician may withhold any of the drugs per their discretion and discussion with the principal investigator as needed to maintain patient safety while a toxicity is evaluated and treated. The drug should be resumed after appropriate toxicity management and dose reduced, if indicated as per Section 10 of the protocol.

Patients must receive at least 80% of the scheduled doses of each study medication to be considered evaluable for DLT. Patients with ER+ breast cancer must receive at least 80% of the scheduled dose of AI to be considered evaluable for DLT. However, any patient who experiences DLT, will be counted as a DLT regardless of how many doses received.

As study therapy is given continuously, missed days of treatment will not be made up. A cycle is defined as 28 days regardless of the number of days of treatment received.

In the event the patient experiences intolerable side effect(s) attributed to the endocrine therapy agent(s), the treating physician may withhold the agent per their discretion and discussion with the principal investigator as needed to maintain patient safety while a toxicity is evaluated and treated. The treating physician may change the AI agent administered and prescribe treatment for symptom control, as clinically indicated.

The following delays are allowed except during the DLT assessment period:

- 1) Up to 4 weeks due to study related AEs
- 2) Up to 8 weeks due to non-study related AEs

Unanticipated Dose Interruptions:

Interruptions due to non-study related issues (logistical, natural disaster, etc) are permitted in the case of logistical reasons not related to study therapy, up to 2 cycles of study.

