10.0 Common Toxicity and Dose Modification

10.1 Neratinib Dose Modifications and Management – General Toxicities

For toxicities deemed to be related to neratinib, follow Table 10.

Table 10: Neratinib Dose Modifications and Management – General Toxicities*

Severity of Toxicity [†]	Action
Grade 3	Hold NERLYNX until recovery to Grade ≤ 1 or baseline within 3 weeks of stopping treatment. Then resume NERLYNX at the next lower dose level.
Grade 4	Discontinue NERLYNX permanently.

* Refer to Tables 13, 14 below for management of diarrhea and hepatotoxicity

† Per CTCAE v5.0

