10.4 Neratinib Dose Modifications for Hepatic Impairment

Guidelines for dose adjustment of neratinib in the event of liver toxicity are shown in Table 13. Patients who experience \geq Grade 3 diarrhea requiring IV fluid treatment or any signs or symptoms of hepatotoxicity, such as worsening of fatigue, nausea, vomiting, right upper quadrant pain or tenderness, fever, rash, or eosinophilia, should be evaluated for changes in liver function tests. Fractionated bilirubin and prothrombin time should also be collected during hepatotoxicity evaluation.

Table 13: Dose Modifications for Hepatotoxicity

Severity of Hepatotoxicity*	Action

 Grade 3 ALT or AST ($>5-20 \times$ ULN) OR Grade 3 bilirubin ($>3-10 \times$ ULN) 	
 Hold NERLYNX until recovery to \leqGrade 1 Evaluate alternative causes Resume NERLYNX at the next lower dose level if recovery to \leqGrade 1 occurs within 3 weeks. If Grade 3 ALT or AST, or bilirubin occurs again despite one dose reduction, permanently discontinue NERLYNX

 Grade 4 ALT or AST ($>20 \times$ ULN) OR Grade 4 bilirubin ($>10 \times$ ULN) 	
 Permanently discontinue NERLYNX Evaluate alternative causes

ALT=Alanine Aminotransferase; AST=Aspartate Aminotransferase; ULN=Upper Limit Normal

* Per CTCAE v5.0

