Grade 1 (> ULN - 1.5 x ULN)	Maintain dose level
Grade 2 (> 1.5 - 3.0 x ULN)	Omit dose until resolved to ≤ grade 1 or baseline, then resume treatment at the same dose level.
Grade 3 (> 3.0 - 6.0 x ULN)	Omit dose until resolved to ≤ grade 1 or baseline, then resume treatment at ↓ 1 dose level.
Grade 4 (> 6.0 x ULN)	Permanently discontinue participant from capmatinib treatment
HEPATIC	
Isolated Total Bilirubin elevation*	
Grade 1 (> ULN - 1.5 x ULN)	Maintain dose level

Grade 2 ($> 1.5 - 3.0 \times \text{ULN}$)	Omit dose until resolved to \leq grade 1, then If resolved in ≤ 7 days, maintain dose level. If resolved in > 7 days, $\downarrow 1$ dose level
Grade 3 ($> 3.0 - 10.0 \times \text{ULN}$)	Omit dose until resolved to \leq grade 1, then If resolved in ≤ 7 days, $\downarrow 1$ dose level If resolved in > 7 days, permanently discontinue participant from capmatinib treatment
Grade 4 ($> 10.0 \times \text{ULN}$)	Mandatory: Permanently discontinue participant from capmatinib treatment
Isolated AST or ALT elevation	
Grade 1 ($> \text{ULN} - 3 \times \text{ULN}$)	Maintain dose level
Grade 2 ($> 3.0 - 5.0 \times \text{ULN}$)	Maintain dose level
Grade 3 ($> 5.0 - 20.0 \times \text{ULN}$)	Omit dose until resolved to \leq grade 1 (or \leq grade 2 if grade 2 elevation at baseline) then If resolved in ≤ 7 days, then resume treatment at the same dose level If resolved in > 7 days, resume treatment at $\downarrow 1$ dose level
Grade 4 ($> 20.0 \times \text{ULN}$)	Mandatory: Permanently discontinue participant from capmatinib treatment
Combined elevations of AST or ALT and Total Bilirubin ^{b,c,d}	
For participants with normal baseline ALT and AST and total bilirubin value: AST or ALT $> 3.0 \times \text{ULN}$ combined with total bilirubin $> 2.0 \times \text{ULN}$ without evidence of cholestasis or hemolysis OR For participants with elevated baseline AST or ALT or total bilirubin value: [AST or ALT $> 3 \times \text{baseline}$] OR [AST or ALT $> 8.0 \times \text{ULN}$], whichever is lower, combined with [total bilirubin $> 2 \times \text{baseline}$ AND $> 2.0 \times \text{ULN}$] without evidence of cholestasis or hemolysis	Mandatory: Permanently discontinue participant from capmatinib treatment
METABOLIC	
Amylase and/or lipase elevation	
Grade 1 ($> \text{ULN} - 1.5 \times \text{ULN}$)	Maintain dose level
Grade 2 ($> 1.5 - 2.0 \times \text{ULN}; > 2.0 - 5.0 \times \text{ULN}$ and asymptomatic)	Maintain dose level

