Grade 3	
Omit dose until resolved to \leq grade 1, then:
 
If resolved in \leq 7 days, resume treatment at same dose level
 
If resolved in $>$ 7 days, resume treatment at \downarrow 1 dose level

Peripheral edema	
Grade 1 or 2	Maintain dose level.
Grade 3	Omit dose until resolved to \leq Grade 1, then \downarrow 1 dose level
Grade 4	Permanently discontinue capmatinib
Other adverse events	
Grade 1 or 2	
Maintain dose level, consider to initiate appropriate support medication.
 
For any intolerable grade 2 (e.g. limiting instrumental ADL), consider omitting the dose until resolved to \leq grade 1, then then restart either at same dose or \downarrow 1 dose level.

Grade 3	Omit dose until resolved to \leq grade 1, then \downarrow 1 dose level
Grade 4	Permanently discontinue capmatinib

All dose modifications should be based on the worst preceding toxicity.
 
a Common Toxicity Criteria for Adverse Events (CTCAE version 5.0).
 
b “Combined” defined as: total bilirubin increase to the defined threshold concurrently with ALT/AST increase to the defined threshold
 
c “Cholestasis” defined as: ALP elevation ($>$ 2.0 x ULN and R value (ALT/ALP in x ULN) $<$ 2.0) in participants without bone metastases, or elevation of ALP liver fraction in participants with bone metastases
 
d If combined elevations of AST or ALT and total bilirubin do not meet the defined thresholds, please follow the instructions for isolated elevation of total bilirubin and isolated elevation of AST/ALT, and take a conservative action based on the degree of the elevations (e.g. discontinue treatment at the situation when omit dose is needed for one parameter and discontinue treatment is required for another parameter). After all elevations resolve to the defined thresholds that allow treatment re-initiation, re-start the treatment either at the same dose or at one dose lower if meeting a criterion for dose reduction
	

* Note: If total bilirubin $> 3.0 \times$ ULN is due to the indirect (non-conjugated) component only, and hemolysis as the etiology has been ruled out as per institutional guidelines (e.g., review of peripheral blood smear and haptoglobin determination), then \downarrow 1 dose level and continue treatment at the discretion of the investigator.

** Note: antidiarrheal medication is recommended at the first sign of abdominal cramping, loose stools or overt diarrhea

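### Eligibility accepts Gilbert bilirubin up to 3 × ULN and liver-metastasis AST/ALT up to 5 × ULN, but Table 15's isolated-bilirubin rows and Table 13's restart rule make no allowance for those baselines

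*Combined protocol and SAP*

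**What the plan says.** **Eligibility (Section 6.1, item 10).** Total bilirubin must not exceed ULN, with one exception: "Patients with known Gilbert disease who have serum bilirubin level" no higher than 3 × ULN may be enrolled. AST and ALT may be up to 3 × ULN, "except for participants with liver metastasis, who may only be included if AST" is at most 5 × ULN; the ALT limit is the same.

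**Capmatinib (Section 10.5.2, Table 15).** For isolated bilirubin of Grade 2 (above 1.5 and up to 3.0 × ULN) the instruction is "Omit dose until resolved to" Grade 1 or lower. The Grade 3 row has the same recovery target. Neither row refers to baseline. A note relaxes the rule when bilirubin above 3.0 × ULN "is due to the indirect (non-conjugated) component only" and hemolysis is excluded: treatment may then continue one level lower at the investigator's discretion. For isolated AST/ALT, Grade 2 (above 3.0 and up to 5.0 × ULN) requires no hold, and restart after Grade 3 is allowed at Grade 2 or lower "if grade 2 elevation at baseline". The row for combined elevations also has separate thresholds for patients with raised baseline values.

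**Neratinib (Section 10.4, Table 13).** For Grade 3 AST/ALT (above 5 × ULN) or Grade 3 bilirubin (above 3 × ULN): "Hold NERLYNX until recovery to" Grade 1 or lower, with restart at the next lower level if that occurs within 3 weeks. Table 13 does not mention baseline. Table 10 (Section 10.1), for general neratinib toxicity, accepts recovery to Grade 1 or lower "or baseline within 3 weeks of stopping treatment", but refers hepatotoxicity to a separate table.

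**DLT evaluability (Section 7.3).** "Patients must receive at least 80% of the scheduled doses of each study medication to be considered evaluable for DLT". A patient who has a DLT is counted whatever the number of doses taken.

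**The concern.** Item 10 deliberately opens the trial to two groups with abnormal liver tests. The dose-modification tables should then say what happens when such a patient shows no more than the value accepted at entry. For isolated bilirubin under capmatinib, and for restart of neratinib, they do not.

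Read as printed, an eligible Gilbert patient can meet a capmatinib hold with no change from baseline. After a Grade 3 liver event, a patient from either group can be back at baseline and still fail the neratinib restart rule. A liver-metastasis patient in that position could restart one study drug and not the other. Sites would have to improvise, and the combination exposure on which DLT evaluability depends could vary with local reading.

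**Working it through.** No sample size, power or error rate is at issue. The check compares each accepted baseline range with each hold trigger and restart threshold.

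**Inputs.** Entry limits are from Section 6.1, item 10. Hold and restart rules are from Tables 13 and 15. Table 13 prints cut-offs for Grades 3 and 4 but none for Grade 1, so I use Table 15's Grade 1 upper limits: 1.5 × ULN for bilirubin and 3 × ULN for AST/ALT. Both tables cite CTCAE v5.0.

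| Drug and test | Baseline range opened by the exception | Hold starts | Held at entry? | Restart needs | Reachable by return to baseline? |
|---|---|---|---|---|---|
| Capmatinib, bilirubin (Gilbert) | >1.5–3.0 × ULN | >1.5 × ULN | Yes | ≤1.5 × ULN | No |
| Neratinib, bilirubin (Gilbert) | >1.5–3.0 × ULN | >3 × ULN | No | ≤1.5 × ULN | No |
| Capmatinib, AST/ALT (liver metastases) | >3–5 × ULN | >5 × ULN | No | ≤5 × ULN if Grade 2 at baseline | Yes |
| Neratinib, AST/ALT (liver metastases) | >3–5 × ULN | >5 × ULN | No | ≤3 × ULN | No |

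An entry value is itself a hold trigger in 1 of 4 cells. Restart cannot be reached by returning to baseline in 3 of 4.

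**Ordering within Table 15.** Take purely indirect bilirubin with hemolysis excluded. At 2 × ULN the Grade 2 row applies: omit until 1.5 × ULN or lower. Above 3.0 × ULN the note applies: continue one level lower, at discretion. The lower value gets the stricter handling.

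**DLT evaluability in Phase Ib.** The window is 56 days and 80% of each drug is required.

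- Allowed missed time: 0.20 × 56 = 11.2, so 11 whole days.
- At 11 missed days: 45/56 = 80.4% taken, evaluable.
- At 12 missed days: 44/56 = 78.6% taken, not evaluable unless a DLT occurred.

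The date depends on when the hold starts. From day 1, the twelfth missed day is day 12. The study calendar (Section 7.10, note c) does not repeat chemistry if it was done within about 8 days before treatment starts. A hold might therefore first be triggered at Cycle 2, nominally day 29, and the twelfth missed day is then 29 + 11 = day 40.

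**The case against.** The strongest reply is that Table 15 compels nothing here. It is introduced as recommended unless a row is marked mandatory, and the bilirubin Grade 2 row is not. It is titled for adverse drug reactions, while Section 12.1.1 covers new events and prior conditions that have worsened, which a stable Gilbert value is not. Section 7.3 leaves holding a drug to physician discretion. This stands as far as it goes: the documents do not show compulsory removal at entry. But the table prints fixed multiples of ULN and states baseline exceptions in other rows, so a site has no written rule for a group that item 10 names. The recommended status does not extend to Table 13.

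It is also fair that Tables 13 and 15 govern different drugs. Different restart rules are not in themselves a contradiction, and Table 10's baseline wording does not reach hepatotoxicity. The gap is between each rule and the eligibility limits.

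Several stronger readings might be inferred and are not supported:

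- *The tables contain no baseline allowance at all.* Table 15 has one for AST/ALT after Grade 3 and another in the combined row.
- *Liver-metastasis patients are on hold at entry.* None is, for either drug.
- *Such patients drop out of the DLT count after a Grade 3 AST/ALT rise.* If at least possibly related and within 56 days, that rise is itself a DLT under Section 7.4 and stays counted.
- *Gilbert bilirubin triggers the Hy's Law DLT.* All its criteria are required, including raised AST or ALT and no other explanation.
- *A third of a cohort is lost, or each patient costs 1/29 of the response rate.* Dose decisions count evaluable patients (Section 13.1), and evaluability for response in Phase II is not defined, so neither effect is established.

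**Conclusion.** The point holds in limited form. Table 15's isolated-bilirubin rows do not fit the Gilbert exception: the Grade 2 hold band coincides with baselines above 1.5 and up to 3.0 × ULN, and the indirect-bilirubin note begins only where that band ends. Table 13's restart rule does not fit either admitted group.

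The statistical consequence is small and confined mainly to Phase Ib. A Gilbert patient held under Table 15 could exceed the 11-day allowance and become non-evaluable, with replacement and delay as the likely result. The documents give no frequency for either group, so the number affected cannot be estimated.

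The conclusion assumes that grades follow the printed multiples of ULN, that Table 15's Grade 1 limits apply to Table 13, and, for the evaluability effect, that a site follows the recommended hold on an unchanged baseline value.

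**What to change.** Reconcile Section 6.1, item 10, with Table 13 and with Table 15's isolated-bilirubin rows and indirect-bilirubin note. An entry value that the protocol accepts should not itself be a hold trigger or make restart unreachable; if either result is intended, the protocol should say so explicitly. The sponsor's medical monitor decides which limits stand. No threshold or clinical rule is proposed here.

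The cost is an amendment to the wording of these items. No extra tests are needed, because baseline liver tests are already collected.
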